## **2 Introduction**

This document describes the planned data statistical analysis of an post-marketing, observational, multicenter, real world evidence study of the effectiveness of Paritaprevir/r – Ombitasvir ± Dasabuvir ± Ribavirin in patients with chronic hepatitis C in the Russian Federation (HCV RWE).

This SAP is written according to ICH E9 Guideline [1] and Data MATRIX LLC SOP [2] using the Protocol Final version 4.0 dated 11 July 2017 and CRF Final version 2.0 dated 25 May 2016.

The purpose of this document is to provide a more technical and detailed elaboration of the principal features of the analysis, described in the Protocol, and to include detailed procedures for executing the statistical analysis.

The SAP needs to be finalized and signed prior to database soft lock. Revisions to the approved SAP may be made prior to database soft lock. In case of deviation from the finalized SAP, explanation will be provided in the CSR.

## **3 Study objectives and variables**

### **3.1 Study Objectives**

The research question of this study: what is the effectiveness, patient reported outcome, work productivity and healthcare resource utilization of the interferon-free ABBVIE REGIMEN ± ribavirin (RBV) in patients with CHC in a real life setting across clinical practice patient populations?

#### **3.1.1 Primary objective**

The Protocol defines the following primary objective of this study:

- to describe in routine clinical practice the effectiveness of the interferon-free ABBVIE REGIMEN ± RBV in patients with CHC as evidenced by Sustained Virological Response at Week 12 after End of Treatment (SVR12).

#### **3.1.2 Secondary Objectives**

The Protocol defines the following secondary objectives of this study:

- to provide real world evidence for predictive factors of virological response;
- to collect information on co-morbidities and concomitant medication in the Russian population;
- to describe the tolerability of the ABBVIE REGIMEN ± RBV;
- to document the effect of the ABBVIE REGIMEN ± RBV on patient-reported outcomes (PROs) and work productivity in the Russian population;
- to determine the impact of the ABBVIE REGIMEN ± RBV on healthcare resource utilization.

---

 This section is based on the sections 8 “Research Question and Objectives”, 9.3 “Variables”, 9.7.3.1 “Primary Effectiveness Endpoints” and 9.7.3.2 “Secondary Effectiveness Endpoints” of clinical study Protocol.

## 3.2 Variables

### 3.2.1 Primary variable

The primary variable of this study (and also effectiveness endpoint) is:

- the percentage of patients achieving SVR12 (single last HCV RNA <50 IU/mL 12 weeks [i.e.  $\geq 70$  days] after the last actual dose of the ABBVIE REGIMEN).

### 3.2.2 Secondary variables

- effectiveness endpoints:
  - the percentage of patients with virological response (HCV RNA <50 IU/mL) at EoT;
  - the percentage of patients with relapse (defined as HCV RNA <50 IU/mL at EoT followed by HCV RNA  $\geq 50$  IU/mL);
  - the percentage of patients with breakthrough (defined as at least one documented HCV RNA <50 IU/mL followed by HCV RNA  $\geq 50$  IU/mL during treatment);
  - the number and percentage of patients meeting each and any of the following SVR12 non-response categories:
    - on-treatment virologic failure: breakthrough (defined as above) or failure to suppress (each measured on-treatment HCV RNA value  $\geq 50$  IU/mL);
    - relapse (defined as HCV RNA <50 IU/mL at EoT or at the last on-treatment HCV RNA measurement followed by HCV RNA  $\geq 50$  IU/mL post-treatment);
    - premature study drug discontinuation with no on-treatment virologic failure;
    - missing SVR12 data and/or none of the above criteria;
- co-morbidities and concomitant medication;
- serious and non-serious adverse events and pregnancy occurrences;
- questionnaires on PROs: EQ-5D-5L questionnaire and WPAI questionnaires prior to treatment initiation at EoT as well as SVR12 and SVR24 (12 and 24 weeks after EoT respectively);
- Patient Activate Measure 13 (PAM-13), patient support program (PSP) satisfaction and utilization questionnaires.

## 4 Study design

### 4.1 General study design and plan

This is a post-marketing, prospective, multicenter, observational study in patients receiving the interferon-free ABBVIE REGIMEN (Paritaprevir/r – Ombitasvir  $\pm$  Dasabuvir) with or without RBV.

This study is focusing on collecting real-world data. Adult patients chronically infected with HCV, receiving the interferon-free ABBVIE REGIMEN will be offered the opportunity to participate in this study during a routine clinical visit at the participating sites. The prescription of a treatment regimen is at the discretion of the physician in accordance with local clinical practice and label, is made independently from this observational study and precedes the decision to offer a patient the opportunity to participate in this study.

---

 This section is based on the sections 9.1 “Study Design”, 9.2.2 “Study duration”, and 9.4.1 “Data to be documented” of clinical study Protocol.

After written informed consent has been obtained, patient data including demographic data, HCV disease characteristics, co-morbidities, co-medication, treatment details, and laboratory assessments as recorded in the patient's medical records (source documentation) will be documented in the eCRF. No patient identifiable information will be captured, a unique patient number will be automatically allocated by the web based eCRF system once the investigator or designee creates a new patient file.

Patients will be observed for the duration of the ABBVIE REGIMEN therapy and for up to 24 weeks after treatment completion. Procedures and diagnostic methods, treatment and follow-up visits will be consistent with physicians' routine clinical practice.

The flowchart of study design is indicated in Figure 1. This schedule is based on the anticipated regular follow-up for patients undergoing treatment for CHC.

[figure not shown]

Figure 4.1 – Study flowchart

As indicated in Figure 1, each patient will be receive 12 or 24 weeks of ABBVIE REGIMEN.

The inclusion period will be approximately 8 months and the observational period of the study will be from baseline visit until 24 weeks post-treatment. The observational period for patients receiving 12 weeks of ABBVIE REGIMEN will be maximum 36 weeks (12 weeks treatment and 24 weeks post-treatment observation) and for patients receiving 24 weeks of ABBVIE REGIMEN the observational period will be maximum 48 weeks (24 weeks treatment and 24 weeks post-treatment observation).

Both regimens include four visits and several time windows for interim data collection (two for 12-week and three for 24-week). Data documented will be those closest to these time windows.

## 4.2 Sample size

The sample size is justified in the clinical study Protocol.

The expected SVR12 rate is 90%. This value is based on results of previous sponsor's studies investigating the interferon-free ABBVIE REGIMEN ± RBV.

 This section is based on the section 9.5 "Study Size" of clinical study Protocol.

The sample size calculation was performed in order to obtain assessments of qualitative features with exact two-sided 95% Clopper-Pearson confidence interval, which doesn't exceed  $\pm 5\%$  (i.e. total spread is not more than 10%) from the point estimate.

With 158 evaluable patients 95% CI will be 84.2%-94.2%, i.e. not more than 10%. Therefore, 158 patients should be enrolled during the inclusion period of 8 months.

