9.5 Study Size

In phase III studies investigating the interferon-free ABBVIE REGIMEN \pm RBV, SVR12 rates of at least 90% were observed, even in difficult-to-treat CHC patients (e.g. cirrhotic G1a treatment experienced patients). To describe in routine clinical practice the effectiveness of the ABBVIE REGIMEN \pm RBV in patients with CHC, a precise estimate of the SVR12 rates in the core population of this study should be achieved (see Section **Error! Reference source not found.** for the definition of the core population).

As obvious from Table 3, if the SVR12 rate is at least 90%, then with 158 evaluable patients the width of the 95% confidence interval (CI) will not be wider than 10%. If the SVR12 rate is at least 95%, then 94 patients are sufficient for a width of 10%. Therefore, 158 patients should be enrolled during the inclusion period of 8 months.

Table 3 Width of 95% Confidence Interval for SVR12

Number of patients	SVR12 rates	95% Confidence Interval*			Width
		Lower Limit	Upper Limit		
158	90%	84.2	94.2		10.0%
94	95%	88.4	98.4		10.0%

* exact two-sided 95% confidence interval according Clopper-Pearson

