In accordance with the non-interventional nature of the study all HCV RNA measurements will be performed at the sole discretion of the physician and all HCV RNA measurements have to be entered into the eCRF. All recorded HCV RNA values will be assigned to appropriate time points (baseline, on-treatment visits, EoT visit, post-treatment visits). The time windows for the assignments will be specified in the statistical analysis plan (SAP).

No data will be imputed for any effectiveness or safety analyses except for the analyses of the HCV RNA endpoints. When there is no HCV RNA value in a visit time window post-baseline, but prior to EoT, the closest values before and after the window, regardless of the value chosen for the subsequent and preceding window, will be used for the flanking imputation described below. If a patient has a missing HCV RNA value at a post-baseline visit prior to EoT but has undetectable HCV RNA (with LLoD ≤ 50 IU/mL) or unquantifiable, but detectable HCV RNA levels (with LLoQ ≤ 50 IU/mL) at both the preceding and succeeding measurements, the HCV RNA level will be considered undetectable or unquantifiable, respectively, at this visit for this patient. In addition, if a patient has an unquantifiable HCV RNA level at the preceding measurement and an

Confidential Information

No use or disclose outside AbbVie is permitted without prior written authorization from AbbVie

Version 3.0 (22 Apr 2015) – country v 1.0 dated 26.06.2015

Page 33 of 61

undetectable HCV RNA level at the succeeding measurement, or vice versa, the HCV RNA level will be imputed as unquantifiable at this visit for this patient. For virological response at EoT a corresponding backward imputation approach will be applied. This means if HCV RNA is missing at EoT, then unquantifiable or undetectable will be assumed for EoT, if the succeeding HCV RNA value is undetectable or unquantifiable. For SVR12 the single last available HCV RNA measurement ≥ 70 days post-treatment will be used. Subsequent to this flanking and backward imputation, if the HCV RNA value remains missing at a specific time point, then the patients will be considered as virological failure at this time point (i.e. not undetectable or unquantifiable).

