9.9 Limitations of the Research Methods

The limitations of observational studies, such as uncontrolled confounding by lack of randomization, and difficulties to clearly interpret treatment effects in the context of missing data are well known. Their validity can be increased by accurate outcome measurements, documentation of the most common confounders, sufficient length of follow-up and by activities to obtain complete recording of available data as well as by searches for missing key data.

The most important outcome measure in this study is HCV RNA. Missing or unrecorded follow-up HCV RNA data can in particular lead to an underestimation of the real SVR rate as compared to the SVR rate of interventional trials. Highly sensitive and quantitative diagnostic tests are required to measure HCV RNA levels in blood. In an observational study each center will be using its own test – either commercially available or so-called “home-brew” tests – which might change from one visit to the next within a patient data set. The challenge is to accurately and consistently document test properties such as the LLoD and the LLoQ to put the results into perspective of prior outcomes from randomized controlled trials with (usually) central laboratory assessments for all trial participants.

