## 6 Analysis populations

*The target population (TP)* – all patients, who fulfill the following criteria:

- treatment-naïve or treatment-experienced adult (age at least 18 years) male or female patients with confirmed CHC with genotype 1 (1a and/or 1b) only, receiving combination therapy with the interferon-free ABBVIE REGIMEN  $\pm$  RBV according to standard of care and in line with the current local label. The prescribed ABBVIE REGIMEN needs to be known;
- if RBV is co-administered with the ABBVIE REGIMEN, it has been prescribed in line with the current local label (with special attention to contraception requirements and contraindication during pregnancy);
- patients with voluntarily signed and dated a patient authorization to use and/or disclosure his/her anonymized health data (or informed consent) prior to inclusion into the study;
- patients must not be participating or intending to participate in a concurrent interventional therapeutic study.

Patients who prematurely discontinue earlier than  $\leq$ study day 55 (for 12 weeks treatment) or  $\leq$ study day 139 (for 24 weeks treatment) will be used in analyses on the population with actual EoT time point without windowing conventions adjustment for EoT.

*The core population (CP)* – all patients of the TP, who have started the treatment combination recommended in the current local label for their disease characteristics. Patients, who fulfill at least one of the following conditions, will be excluded from the CP:

- patients with unknown fibrosis status;
- cirrhotic patients with genotype 1a not receiving ribavirin;
- patients with genotype 1 for whom two direct-acting antiviral agents regimen (2DAA) instead of 3DAA is prescribed;
- patients with EoT  $\leq$ study day 55 (for 12 weeks treatment) or  $\leq$ study day 139 (for 24 weeks treatment).

*The safety population (SP)* – all patients who received at least one dose of the ABBVIE REGIMEN.

 This table is based on the table 4 “Analysis time windows” of clinical study Protocol.

 These time windows are intended for the CP allocation filter only. In case of the TP, all patients will be used for the analysis regardless of actual EoT day relevance to EoT time windows.

 This section is based on the sections 9.7.1 “Analysis population, time windows and handling of missing data” and 9.2.1 “Target population” of clinical study Protocol.

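### SAP 4.2 claims ±5%, but n = 158 at 90% gives 5.8 below and 4.2 above; and 158 evaluable core-population patients are equated with 158 enrolled

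*SAP*

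**What the plan says.** SAP 4.2 names a planning rate ("The expected SVR12 rate is 90" per cent) and asks for an exact two-sided 95% Clopper-Pearson interval within ±5% of the estimate. The same sentence equates this with a total spread: "i.e. total spread is not more than 10%) from the point estimate". It then states: "With 158 evaluable patients 95% CI will be 84.2%-94.2%, i.e. not more than 10%. Therefore, 158 patients should be enrolled".

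Protocol 9.5 and its Table 3 give the same number and limits but speak only of total width; ±5% does not appear there. The Protocol says which population the target is for: "a precise estimate of the SVR12 rates in the core population of this study should be achieved". It reaches the same enrolment figure: "Therefore, 158 patients should be enrolled during the inclusion period of 8 months".

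The core population (CP) is a subset of those enrolled. Protocol 9.7.1 keeps only target-population patients who started the combination that the local label recommends for them. SAP 6 adds a list: "Patients, who fulfill at least one of the following conditions, will be excluded from the CP". The list covers unknown fibrosis status, two regimen-related conditions, and end of treatment at or before day 55 (12-week course) or day 139 (24-week course). Neither sample size section mentions an allowance for these exclusions.

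**The concern.** The study size rests on this precision statement alone. There is no hypothesis test and no power calculation behind it.

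A half-width of 5 and a total width of 10 are the same criterion only for a symmetric interval. A Clopper-Pearson interval at 90% is longer on the lower side, and that side shows how poor real-world SVR12 could be. A reader of SAP 4.2 would believe that the lower limit lies within 5 points of the estimate, and the claim could be carried into the report.

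The 10-point width is promised for the CP but bought with a count of enrolled patients. If any of the 158 fall outside the CP, the stated width no longer follows at the planning rate.

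**Working it through.** **Inputs.** SVR12 rate 90%, two-sided 95% Clopper-Pearson, n = 158, enrolment 158 (SAP 4.2; Protocol 9.5 and Table 3). The documents give no CP loss rate and no missing-data rate; those used below are assumptions.

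**Formula.** Lower limit = 2.5% quantile of Beta(x, n − x + 1); upper limit = 97.5% quantile of Beta(x + 1, n − x). With x = n × rate, not rounded to a whole number, this reproduces the plan's figures.

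**Step 1: the plan's own figures.**
- n = 158, x = 0.90 × 158 = 142.2: 84.23 to 94.20, width 9.97. This agrees with the stated 84.2 to 94.2.
- n = 94, rate 95%: 88.45 to 98.43, width 9.98. This agrees with the second row of Table 3.
- n = 157, rate 90%: width 10.006. So 158 is the smallest n that meets the width target at 90%.

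**Step 2: the ±5% statement.**
- Below the estimate: 90 − 84.23 = 5.77. Above it: 94.20 − 90 = 4.20. The lower arm exceeds 5.
- Smallest n with a lower arm of at most 5 at 90%: 202 (limits 85.01 and 93.77).
- With n = 158 the lower arm falls to 5 only at an observed rate of about 93.7%.

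**Step 3: whole counts.** 142/158 (89.9%) gives 84.08 to 94.10, width 10.02. 143/158 (90.5%) gives 84.83 to 94.59, width 9.76. So the width exceeds 10 when 142 or fewer respond. With all 158 in the CP, the binomial probability of that is 52% if the true rate is 90%, 20% at 92% and 0.6% at 95%.

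**Step 4: CP smaller than enrolment (assumed losses).**

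| Assumed loss | CP size | Width at 90% | Width at 92% | Width at 95% | Rate from which width ≤ 10 |
|---|---|---|---|---|---|
| 5% | 158 × 0.95 ≈ 150 | 10.25 | 9.36 | 7.70 | 90.6% |
| 10% | 158 × 0.90 ≈ 142 | 10.55 | 9.63 | 7.94 | 91.2% |
| 15% | 158 × 0.85 ≈ 134 | 10.88 | 9.94 | 8.19 | 91.9% |

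**Step 5: missing SVR12.** Where no value can be filled in, Protocol 9.7.1 rules: "then the patients will be considered as virological failure at this time point". This keeps the denominator but lowers the observed rate. With 5% missing (assumed) the rate becomes 0.90 × 0.95 = 85.5%, and with 10% it becomes 0.90 × 0.90 = 81%. At n = 158 the widths are 11.6 (79.03 to 90.59) and 12.8 (74.00 to 86.80).

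**The case against.** The strongest reply is that ±5% is only a loose paraphrase. The SAP explains it as total spread in the same sentence, prints the true limits straight afterwards, and refers to the Protocol, which uses width alone; the n, limits and width all reproduce. That is right about the n: 158 is correct for the width criterion. It does not rescue the sentence, which equates two different criteria and is contradicted by the interval that follows it.

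Several points on the second part stand:
- Protocol 9.5 treats 90% as a floor, and most trial rates it cites are higher. At 92% only 133 patients are needed, so a 15% loss is absorbed. But 90% is the rate the SAP names as expected.
- Eligibility already requires treatment in line with the local label, which overlaps part of the CP definition. Unknown fibrosis status and early end of treatment remain.
- The 52% in Step 3 includes 142/158, whose width of 10.02 prints as 10.0. Without that count it is 41% at 90% and 13% at 92%.
- The missing-data effect is a separate mechanism, and Protocol 9.9 acknowledges it: "Missing or unrecorded follow-up HCV RNA data can in particular lead to an underestimation of the real SVR rate". That section does not link it to the precision target.
- SAP 2.0 is dated February 2018, after the planned end of data collection in August 2017, so the sensitivity widths cannot guide enrolment. The SAP also cites Protocol version 4.0, whereas the Protocol reviewed here is version 3.0, so Protocol 9.5 may have changed. Neither point affects SAP 4.2's own wording.

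**Conclusion.** The concern holds on both parts. The ±5% statement is false at the planning rate by the SAP's own figures (5.8 below, 4.2 above); this needs no outside assumption. The 10-point width is met only if all 158 enrolled patients enter the CP, and at 90% there is no slack.

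The size is modest. Assumed CP losses of 5 to 15% add about 0.3 to 0.9 points of width at 90%, and the target still holds at 92%. A lower observed rate through missing data would cost more, about 1.6 to 2.8 points under the assumed rates. Because the analysis is descriptive and exact intervals will be reported, what is wrong is the stated design property; the estimate and its interval are unaffected. It should be corrected because nothing else supports the sample size.

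**What to change.** Change the wording of SAP 4.2 and leave enrolment as it is:

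1. Delete ±5% and state that with 158 patients in the CP and an observed SVR12 of 90%, the exact 95% interval is 84.2 to 94.2: 5.8 points below, 4.2 above, total width 10.0.
2. Say that 158 is the required CP size and that the enrolment figure contains no allowance for CP exclusions. Add a matching note to Protocol 9.5, after checking the text of the version now in force.
3. Preferably add one line, labelled as assumptions, giving the width for a CP of 150, 142 or 134 (10.3, 10.6, 10.9 at 90%; 9.4, 9.6, 9.9 at 92%) and for a lower observed rate when missing counts as failure (11.6 at 85.5%; 12.8 at 81%). The correction does not depend on this line.

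The cost is a few lines of text. Data collection and analysis do not change; the stated precision becomes slightly less favourable.

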### **4.3 Randomization and blinding**

This study is observational. Randomization and blinding procedures are not applicable.

### **4.4 Planned analyses**

The only final statistical analysis report will be performed for this study. No analyses for DMC meetings and no interim analysis are planned in the study.

## **5 General considerations**

### **5.1 Reference start date/time, study day, baseline**

Study Day will be calculated from the reference start date, and will be used to show start/stop day of assessments and events.

Reference start date is defined as the day of the ABBVIE REGIMEN start treatment ("EXSTDTC" variable from "EX" domain of the database where "EXTRT" equal "ABBVIE REGIMEN").

If the date of the event is on or after the reference date then  
$$\text{study day} = (\text{date of event} - \text{reference date}) + 1.$$

If the date of the event is prior to the reference date then  
$$\text{study day} = (\text{date of event} - \text{reference date}) - 1.$$

Baseline value is defined as the measurement taken on Baseline visit, unless otherwise specified.

### **5.2 Windowing conventions**

Due to exploratory nature of the study all interim time-points will be separated into visits in the analysis stage. The most detailed possible situation is:

- on-treatment Week 4 from 15 to 42 study days;
- on-treatment Week 8 from 43 to 70 study days;
- on-treatment Week 12 from 71 to 98 study days;
- on-treatment Week 16 from 99 to 126 study days;
- post-treatment Week 4 from 15 to 56 days post EoT.

Table 5.1 describes assignment of time point windows to the following data for purposes of effectiveness, safety and tolerability analyses.

Table 5.1 – Analysis time windows

| Time point             | Time Window  |                        |
|------------------------|--|------------------------|
|                        | 12 weeks treatment   | 24 weeks treatment     |
| Baseline        | Last value prior to start of study treatment (i.e. $\leq$ study day 1) |                        |
| EoT | Last value between   |                        |
|                        | 56 and 98 study days   | 140 and 182 study days |
| SVR12           | Last value between 57 and 112 days post the study day of last dose     |                        |
| SVR24           | Last value between 141 and 196 days post the study day of last dose    |                        |

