9.7.3.1 Primary Effectiveness Endpoint

The percentage of patients achieving SVR12 (single last HCV RNA <50 IU/mL 12 weeks [i.e. at least 70 days] after the last actual dose of the ABBVIE REGIMEN) is the primary effectiveness endpoint.

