9.7.4 Clinical Laboratory Data

All reported clinical laboratory test results will be assigned to one of the time points using the time windows specified in the table below.

Table 4 - Analysis Time Windows

Phase	Time point	Time Window
Pre-Treatment	Baseline	Last value prior to start of study treatment (i.e. \leq study day 1)
Treatment Weeks		Study day during treatment period (Study day 1 = first treatment day)
	4 (day 29)	15 – 42
	8 (day 57)	43 – 70
	12 (day 85)	71 – 98
	16 (day 113)	99 – 126
EoT	Actual EoT	Study day of last dose (28 days prior to EoT - 14 days post EoT)
Post Treatment	4 weeks (day 29 post EoT)	15 – 56 post EoT
	12 weeks (day 85 post EoT)	57 – 112 post EoT
	24 weeks (day 169 post EoT)	141 – 196 post EoT

Mean changes from baseline to each post-baseline visit will be summarized descriptively.

Laboratory data values collected during the treatment period will be categorized as low, normal, or high based on reference ranges used in this study. The number and percent of patients who experience post-baseline shifts during treatment in clinical laboratory values from low/normal to high and high/normal to low based on the reference range will be summarized.

Additional details of the analyses of clinical laboratory data will be specified in the SAP.

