P15-743 (HCV RWE)\_ STATISTICAL ANALYSIS PLAN \_ Final 2.0 \_ 02 Feb 2018

The non-core population (NCP) – patients not receiving the treatment recommended in the local label (patients with EoT ≤study day 55 for 12 weeks treatment and patients with EoT ≤study day 139 for 24 weeks treatment).

The core population with sufficient follow-up data (CPSFU) – all CP patients, who fulfil one of the following criteria:

- evaluable HCV RNA data ≥70 days after the last actual dose of the ABBVIE REGIMEN (i.e. data within the SVR12 time window);
- a HCV RNA value ≥50 IU/mL at the last measurement post-baseline (i.e. no virological response achieved at the last measurement on-treatment or post-treatment);
- HCV RNA <50 IU/mL at the last measurement post-baseline, but no HCV RNA measurement ≥70 days after the last actual dose of the ABBVIE REGIMEN due to reasons related to safety (e.g. dropped out due to AE) or incomplete efficacy information (e.g. virologic failure such as relapse is reported in the eCRF but date and value of the corresponding HCV RNA test is missing).

In this way, only patients who had virological response at their last on-treatment or post-treatment measurement, but had no HCV RNA measurements ≥70 days post-treatment for reasons not related to safety or effectiveness (e.g. lost-to-follow-up or patient not willing to perform an additional HCV RNA test ≥70 days post-treatment) will be excluded from this analysis.

Figure 6.1 illustrates the patients selection for CPSFU.

[figure not shown]

Figure 6.1 – The core population with sufficient follow-up data (CPSFU) allocation

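### SAP Table 5.1 takes SVR12 from days 57–112 after the last dose, but the primary endpoint is the last HCV RNA at 70 days or later with no upper limit

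*SAP*

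**What the plan says.** The protocol defines the primary endpoint in 9.7.3.1 as "single last HCV RNA <50 IU/mL 12 weeks [i.e. at least 70 days] after the last actual dose of the ABBVIE REGIMEN". Protocol 9.7.1 also fixes which value to use: "For SVR12 the single last available HCV RNA measurement ≥ 70 days post-treatment will be used". Neither sets an upper limit. SAP 3.2.1 repeats the definition ("single last HCV RNA <50 IU/mL 12 weeks", with the 70-day minimum in brackets). SAP 8.1 and shell Table 1.2 count patients by the same 70-day cut-off. The first CPSFU criterion in SAP 6 is "evaluable HCV RNA data ≥70 days after the last actual dose of the ABBVIE REGIMEN (i.e. data within the SVR12 time window", which treats the 70-day rule and the SVR12 window as the same thing.

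SAP 5.2 says something different. Table 5.1, stated to apply "for purposes of effectiveness, safety and tolerability analyses", gives the SVR12 row as "Last value between 57 and 112 days post the study day of last dose" and the SVR24 row as days 141–196. A footnote says the table is based on protocol Table 4. Protocol 9.7.4 introduces that table for another purpose: "All reported clinical laboratory test results will be assigned to one of the time points using the time windows specified in the table below".

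SAP 9 and shell Table 2.1.1.1.1 describe SVR12 as 12 weeks after the last dose and omit the 70-day minimum. SAP 16 states that the methods fully agree with the protocol.

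**The concern.** A window built for laboratory safety values has been carried over to the primary endpoint, where it conflicts with the endpoint definition at both ends. At the early end it admits results that the definition regards as premature. At the late end it drops results that the definition says must be used, including late positives that turn a responder into a failure. SAP 9, the section a programmer works from, no longer mentions 70 days, so Table 5.1 is the only explicit timing rule for that derivation.

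Off-window tests are to be expected, because protocol 9.7.1 leaves the timing of HCV RNA measurements to the physician. The errors run in opposite directions: valid cures become missing, while premature negatives and later relapses count as cures. An unremarkable overall rate would therefore not reveal the problem.

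**Working it through.** **The plan's precision figure.** Inputs: n = 158 and SVR12 = 90% (protocol 9.5, SAP 4.2), exact two-sided 95% Clopper-Pearson interval. With x = 0.90 × 158 = 142.2, the lower limit is the 2.5% quantile of Beta(x, n − x + 1) and the upper limit is the 97.5% quantile of Beta(x + 1, n − x). The result is 84.2% to 94.2%, width 9.97 points, which reproduces the plan. The planned margin is ±5 points.

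**Day counts.**
- SAP window: 112 − 57 + 1 = 56 days.
- Before the 70-day minimum: 69 − 57 + 1 = 13 days, and 13/56 = 23%.
- In neither the SVR12 nor the SVR24 window: 140 − 113 + 1 = 28 days.
- Qualifying days up to week 24 (day 168): 168 − 70 + 1 = 99. Of these, 168 − 113 + 1 = 56 lie outside the SVR12 window.

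These are calendar counts, not shares of patients.

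**Three patients under each rule.**

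| HCV RNA after last dose | 70-day rule | Table 5.1 | Consequence |
|---|---|---|---|
| Only a day-60 negative, then lost to follow-up | Missing, so failure (protocol 9.7.1) | Responder | Responder in the CP, excluded from CPSFU |
| Only late test is a day-120 negative | Responder | No value, SVR12 missing | In CPSFU and counted in Table 1.2 as assessed, but missing in Table 2.1.1.1.1 |
| Negative at EoT and day 80, positive at day 120 | Failure | Responder | Also meets the SAP relapse definition, so is both responder and non-responder in one table |

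**Illustration (numbers of patients assumed).** Each reclassified patient moves the rate by 1/158 = 0.63 points.
- Suppose 150 of 158 are responders under the 70-day rule, and 8 of them have their only qualifying value after day 112. The rate is 150/158 = 94.9% (90.3–97.8) under that rule. Under Table 5.1 with missing counted as non-response it is 142/158 = 89.9% (84.1–94.1).
- Suppose instead that 8 of 150 Table 5.1 responders have only a day 57–69 negative. Table 5.1 then gives 94.9% where the 70-day rule, with missing as failure, gives 89.9%.

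**Range, starting from 142/158 = 89.9%.** For late-only patients this is the rate under the 70-day rule, and about 90% of them (3, 7 and 14) are taken as responders. For early-only responders it is the rate under Table 5.1.

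| Patients affected | Late-only: Table 5.1, missing = failure | Late-only: Table 5.1, missing excluded | Early-only: 70-day rule, missing = failure |
|---|---|---|---|
| 3 (2%) | 139/158 = 88.0% | 139/155 = 89.7% | 139/158 = 88.0% |
| 8 (5%) | 135/158 = 85.4% | 135/150 = 90.0% | 134/158 = 84.8% |
| 16 (10%) | 128/158 = 81.0% | 128/142 = 90.1% | 126/158 = 79.7% |

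**The case against.** The best defence is that the two rules can be read together: Table 5.1 assigns values to visits, SAP 3.2.1 defines the endpoint, and applying both gives days 70–112. The early error then disappears. No section states that combination, however, and it would still drop values after day 112, contrary to the last-available rule.

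Other points limit the size of the problem:
- Footnotes to the effectiveness shells say the CP and CPSFU contain the same patients. If so, few patients with only a day 57–69 negative can exist. The text after those shells makes the equality conditional, so this cannot be relied on.
- The SAP also plans Table 2.1.1.1.3, without patients whose SVR12 is missing. There the late-only illustration gives 142/150 = 94.7%, almost no shift. That table is supplementary. In the main CP table missing SVR12 sits among the non-response categories.
- Values on days 141–196 feed SVR24, and the relapse definition has no window, so a late relapse is still reported. It is misclassified for SVR12, not hidden.
- Protocol 9.7.1 delegates HCV RNA windows to the SAP. The same section nevertheless fixes the SVR12 value separately.
- The SAP cites protocol version 4.0, whereas the protocol available here is version 3.0 (country version 1.0). Version 4.0 could not be checked, but the conflict exists inside the SAP alone, between 5.2 and sections 3.2.1 and 6.

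What stands is that the size is unknown and the early-end error may be small. The conflict itself remains.

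**Conclusion.** The concern holds. Table 5.1 is a stated rule that misderives the primary endpoint, and it contradicts the SAP's own definition as well as the protocol's. The day counts rest on the documents alone. The percentage shifts rest on assumed numbers of patients tested outside days 70–112 and, for the full shift, on counting missing SVR12 as non-response. Under those assumptions about 8 of 158 patients are enough to move the estimate by as much as the study's planned margin of precision. Because individual primary outcomes turn on which section is followed, this should be settled before the analysis is run.

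**What to change.** In Table 5.1, for HCV RNA endpoints only, replace the SVR12 row with the last available HCV RNA measurement at 70 days or more after the last actual dose. State that days 57–112 apply only to laboratory safety data and questionnaires. Restore the 70-day minimum in SAP 9 and in the effectiveness shells, and use one common flag for SVR12, CPSFU and Tables 1.2 and 2.1.x. If an upper limit is really wanted, it changes the primary endpoint and should be declared in SAP 16 and written consistently into SAP 3.2.1, 6 and 9.

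The cost is one table row and one derivation, with matching wording elsewhere. No new data are needed and the sample size is unaffected. SAP 2 allows revision before database soft lock; after that, the departure has to be explained in the study report.
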